9.2 Physical Examination, Height, Vital Signs

Physical examination will include general appearance, cardiovascular, respiratory, abdominal, musculoskeletal, neurological, lymph nodes, and skin. Any findings before first administration of investigational product should be reported in the medical history. Clinically significant findings after first administration of study drug should be reported as AEs.

Height without shoes will be recorded in centimetres.

Vital signs will include body temperature (°C), respiratory rate, radial pulse rate, systolic and diastolic blood pressures. Sitting recordings are to be made after the subject has been sitting for at least 5 minutes with their feet squarely on the floor and arms relaxed, bent at the elbow.

An AE form must be completed for all changes identified as clinically noteworthy.

9.3 12-lead ECG

Standard 12-lead ECGs will be measured after the subject has been resting for minimum of 5 minutes.

All 12-lead ECG recordings (including heart rate, QT, QTcF, QTcB, RR interval, P-wave, QRS complex duration, and PR interval) will be performed and interpreted at study sites by Investigators. ECGs will be planned to coincide with first dialysis of the week. If this is not possible, ECGs should be planned for the same session of the week.

At screening, the Investigator must document clinically relevant ECG findings on the appropriate baseline eCRF pages. Any new clinically relevant ECG finding, or aggravation/worsening of an already existing finding as assessed by the Investigator, must be reported as an AE (see Section 10).

9.4 Clinical Laboratory Tests

The following clinical laboratory tests are to be performed as indicated in the Schedule of Events (Table 1).

- Serum chemistry (central laboratory assessment at screening, local laboratory assessments at subsequent visits)
 - Albumin, bilirubin (total), AP, ALT, AST, glucose, serum creatinine, BUN
 - Electrolytes (sodium, potassium, chloride, calcium, and phosphorus)
- Haematology obtained (central laboratory assessment at screening, local laboratory assessments at subsequent visits)
 - Haemoglobin, haematocrit, platelet count, white blood cell count (including differential)

• Other:

- Serum pregnancy test in women of childbearing potential (central laboratory assessment)

Details on the processing and shipment of specimens are provided in the Laboratory Manual. In the event of an unexplained clinically noteworthy abnormal laboratory test value, the test should be repeated immediately and followed up until it has returned to the normal range and/or an adequate explanation of the abnormality is found.

Details on the clinical laboratories used in this clinical trial, such as address, accreditation certificates, are available in the Trial Master File.

9.5 Adverse Events

See Section 10.

9.6 PK Assessments

PK samples will be obtained from a venous access different from the site of difelikefalin administration to avoid cross contamination. Samples will be obtained at timepoints as noted in Table 1 and Table 2, within the allowed time windows. The exact time of PK samples collection must be recorded.

Details of the procedures to be followed for sample collection, storage, and shipment will be documented in a separate Laboratory Manual.

These samples will not be used to assess biomarkers or genetic markers.

9.7 Dialysis

The HD prescription should be kept constant throughout the study. If the dialysis prescription must be changed or if there is an access problem that precludes achieving the prescribed blood flows, please contact the Medical Monitor. Record procedural data (start and stop times, net ultrafiltration, access changes).

10. EVALUATION, RECORDING, AND REPORTING OF AES

10.1 Definition of AEs

An AE is any untoward medical occurrence in a subject or clinical investigation subject administered a pharmaceutical product and which does not necessarily have a causal relationship with this treatment. An AE can therefore be any unfavourable and unintended sign (including an abnormal laboratory finding), symptom, or disease temporally associated with the use of a medicinal (investigational) product, whether or not related to the investigational product.

10.2 AE Reporting Period

The AE reporting period begins at the time the ICF is signed by the subject. The AE reporting period ends at the last study visit (end of study/early termination). For SAE reporting period, see Section 10.7.2.

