The investigational product will be administered as an IV bolus within 15 minutes after the end of the dialysis session on Days 1, 3, and 5. The investigational product will be administered based on 0.5 μ g/kg of dry body weight. The total dose volume (ml) required from the difelikefalin vial should be calculated as follows: 0.01 × prescription dry body weight (kg), rounded to the nearest tenth (0.1 ml). The investigational product may be given either during or after rinse back of the dialysis circuit. Following the IV push of investigational product, the venous line must be flushed with at least 10 ml of normal saline.

PK samples will be collected on Days 1, 2, 3, 5, 6, 8, 10, and 12. PK samples are to be obtained from a venous access different from the site used for difelikefalin administration to avoid cross contamination.

Vitals signs, physical examinations, 12-lead ECG, clinical laboratory tests will be monitored periodically, and AEs and concomitant medications will be continuously recorded during the study. A final safety follow-up visit will be conducted on Day 14 (up to +3 days).

Sample Size:	This study will enrol 30 subjects.
	The sample size for this Phase 1 study is based on a pragmatic approach. No formal sample size calculation has been conducted.
Study Sites:	1-4 study sites in China
Statistical Methods:	Detailed methodology for summary and statistical analyses of the data collected in this trial will be documented in a Statistical Analysis Plan (SAP), which will be finalised prior to database lock. Any deviation from the SAP will be noted and explained in the clinical study report. All individual data will be listed as measured.
	Frequency tables for categorical variables (absolutes and relative frequencies) and descriptive statistics for continuous variables (i.e., number of subjects, mean standard deviation (SD), minimum, median, quartiles, and maximum) will be calculated. All statistical analyses will be purely descriptive.
	Analysis Populations:
	The following subject populations will be used for presentation and analysis of the data:
	• The safety analysis set (SAF) consists of all enrolled subjects who have received at least 1 dose of investigational product.
	• The PK population is defined as all subjects who have received the investigational product, did not have major protocol deviations or other events that may affect PK, and have sufficient plasma concentration. The PK population will be finalised prior to database lock.

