1.2.2.1 Pharmacokinetics

In subjects with normal renal function, difelikefalin has linear and dose-proportional PK, with t_{1/2} of approximately 2-3 hours after single dose IV administration. In subjects with CKD on HD, t_{1/2} increases at least 10-fold compared with subjects with normal renal function.

Following single dose IV administration of (¹⁴C)-difelikefalin to healthy volunteers or HD subjects, >99% of circulating plasma radioactivity remained as unchanged difelikefalin.

In both healthy volunteers and HD subjects, most of the dose excreted into urine and faeces was unchanged difelikefalin with minor quantities of putative metabolites, none exceeding 2.5%.

In a Japanese clinical pharmacology study in healthy subjects (Study PR-13A9-P1-A), the cumulative urinary excretion rate became almost constant by 36 hours after the initial dose (i.e., 15 hours after the final dose). The cumulative urinary excretion rate for up to 72 hours after the initial dose (i.e., 51 hours after the final dose) ranged from 71.6% to 76.8%, being similar across the dose groups (1.0, 3.0, 5.0, 10, 20, and 40 μ g/kg).

In Japanese HD subjects (Study PR-13A9-P1-B), plasma difelikefalin concentrations after the first and third IV doses showed a biphasic elimination pattern of a rapid initial phase and a slow elimination phase. The $t_{1/2}$ of difelikefalin was 34.1 to 39.0 hours after the first dose and 40.0 to 49.3 hours after the third dose. The accumulation ratio of Day 5 to Day 1 calculated using the C_{max} , AUC_{0-48} , and trough values indicated a low likelihood of accumulation of difelikefalin.

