5.4 Withdrawal of Subjects

5.4.1 Withdrawal of Subjects from the Study

Subjects may voluntarily withdraw from study participation at any time without having to provide a reason. Subjects may be withdrawn because of the appearance of a new health

condition requiring care or medications prohibited by the protocol, unacceptable AEs, refusal to continue treatment, major non-compliance with study procedures, significant protocol deviations, or at the Investigator's discretion if it is in the subject's best interest.

If a subject withdraws from the study at any time either at his or her request or at the Investigator's discretion, the reason(s) for withdrawal must be recorded on the relevant page of the subject's eCRF and source documentation. Subjects who withdraw from the study prematurely should undergo all end of study assessments, if possible.

If a subject is withdrawn from the study due to an AE, it is vital to obtain follow-up data. In any case, every effort must be made to undertake protocol-specified safety follow-up procedures (see Section 10.3). If a subject is discontinued due to an AE, the event should be followed by the Investigator through contact with the subject until resolution or stabilisation has occurred. All AEs should be followed until resolution, stabilisation, or the subject is lost to follow-up and cannot be contacted.

If a subject refuses to continue study procedures, the reason for refusal should be fully documented in the subject's source document and recorded in the study-specific eCRF. Although subjects are not obliged to give a reason for withdrawing consent, the Investigator should make every effort to obtain the reason, while fully respecting the subject's rights. If the subject withdraws from the trial without providing a reason, the source documents and the eCRF should document the reason for discontinuation as "withdrawal by subject".

Subjects who discontinue from the study after administration of the first dose of investigational product and before completing the protocol procedures will not be replaced.

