8.4 Follow-up Procedures

8.4.1 Day 10

- Pre-dialysis blood sample for PK can be taken at any time before starting dialysis. PK samples are to be obtained from a venous access different from the site used for difelikefalin administration to avoid cross contamination
- Dialysis
- Post-dialysis blood sample for PK will be taken at 5 minutes (±2 minutes) following the end of the dialysis. PK samples are to be obtained from a venous access different from the site used for difelikefalin administration to avoid cross contamination
- AEs assessment
- Concomitant medications

8.4.2 Day 12

- Pre-dialysis blood sample for PK can be taken at any time before starting dialysis. PK samples are to be obtained from a venous access different from the site used for difelikefalin administration to avoid cross contamination
- Dialysis
- Post-dialysis blood sample for PK will be taken at 5 minutes (±2 minutes) following the end of the dialysis. PK samples are to be obtained from a venous access different from the site used for difelikefalin administration to avoid cross contamination
- AEs assessment
- Concomitant medications

8.4.3 End of Study (or Early Discontinuation) Procedures/Day 14 (+ up to 3 Days)

On completion of the study (i.e., Day 14 plus up to 3 days), or if subject is discontinued/withdrawn early, a last study visit should be conducted (on a dialysis day) and the following assessments and procedures should be performed:

- Assess vital signs within 6 hours prior to starting dialysis, whenever possible
- Serum chemistry obtained within 6 hours before starting dialysis, whenever possible (local laboratory assessment)
 - Albumin, bilirubin (total), AP, ALT, AST, glucose, serum creatinine, BUN

- Electrolytes (sodium, potassium, chloride, calcium, and phosphorus)
- Serum pregnancy in women of childbearing potential (central laboratory assessment) to be done within 6 hours prior to starting dialysis, whenever possible
- Haematology obtained within 6 hours before starting dialysis, whenever possible (local laboratory assessment)
 - Haemoglobin, haematocrit, platelet count, white blood cell count (including differential)
- AEs assessment
- Concomitant medications

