10.7.2 SAE Reporting

The SAE reporting period begins at the time the ICF is signed by the subject. The SAE reporting period ends 30 days following the last study visit or until 30 days after last investigational product administration, whichever is longer. After last study visit, SAEs that comes to the attention of the Investigator must be reported to the CRO/Sponsor and will be documented in the safety database of the Sponsor only and not in eCRF.

A death occurring during the study, or which comes to the attention of the Investigator within 30 days after the last study visit or until 30 days after the last investigational product administration, whichever is longer, whether considered treatment-related or not, must be reported to the Sponsor (or its delegate, e.g., CRO).

Any SAE considered to have a causal relationship (i.e., related) to the investigational product and discovered by the Investigator at any time after the study should be reported. A rationale for the assessment of a causal relationship must be provided by the Investigator. Any safety information that is obtained after database lock of the clinical database will be documented in the safety database and implications for handling the data in the clinical database assessed on an individual case basis.

The occurrence of an SAE must be immediately reported to the Sponsor (or its delegate, e.g., CRO) within 24 hours of awareness using the study-specific Sponsor SAE form/via SAE CRF/eCRF in the electronic data capture (EDC), or as defined in the study monitoring plan. This includes all SAEs (independent of relationship to study treatment).

The onset date of the SAE is defined as the date the signs and symptoms/diagnosis became serious (i.e., met at least 1 of the criteria for seriousness; see Section 10.7.1). If the condition started as a non-serious event and then became serious, 1 AE and 1 SAE will be recorded. The resolution date of the SAE is defined as when the symptoms resolve, or the event is considered chronic (e.g., sequelae) or stable, and/or if the seriousness criteria are no longer applicable.

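### AE collection ends at the early-termination visit with no minimum time after the last dose, so a dosed early leaver may be observed for as little as 2–3 days against 9–12 for completers

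*Combined protocol and SAP*

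**What the plan says.** - **End of AE collection (Section 10.2).** Collection starts at consent. For its end the section says: "The AE reporting period ends at the last study visit (end of study/early termination". Time since the last dose plays no part.
- **Timing of the last visit (Section 8.4.3).** For completers the visit is "On completion of the study (i.e., Day 14 plus up to 3 days"; otherwise, "if subject is discontinued/withdrawn early, a last study visit should be conducted (on a dialysis day". A footnote to Table 1 repeats the dialysis-day requirement. Neither place says how soon after withdrawal or dosing an early visit falls.
- **Dosing (Synopsis).** Difelikefalin is given "after the end of the dialysis session on Days 1, 3, and 5".
- **SAEs (Section 10.7.2).** These are reportable until 30 days after the last visit or the last dose, whichever is later. Those arising after the last visit "will be documented in the safety database of the Sponsor only and not in eCRF".
- **Withdrawal (Section 5.4.1).** After withdrawal for an AE, "every effort must be made to undertake protocol-specified safety follow-up procedures (see Section 10.3". Section 10.3 deals with how subjects are questioned and what is needed to judge causality. Sections 5.4.1 and 10.5.1 have AEs already on record followed to resolution or stabilisation. Subjects who leave after the first dose are not replaced.
- **Analysis (Sections 12.4.1 and 12.10.1).** The safety set is everyone with at least one dose. AEs count from the first dose onward, with no upper limit relative to the last dose.

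**The concern.** AE incidence is the first-named component of the secondary endpoint and is reported as a percentage of one pooled group of dosed subjects. Such a percentage is easy to read only if everyone in the denominator was observed for a comparable time. Here the window closes earlier for a subject who leaves early, and adverse events are among the listed reasons for withdrawal. Short observation may therefore be related to tolerability.

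The protocol anchors other safety periods to the last dose: SAE reporting (30 days) and contraception (7 days). AE collection has no such anchor and may close after 2 days. At stake are new non-serious AEs, including non-serious events of special interest such as dizziness or somnolence, and the completeness of the SAE tables for early leavers.

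**Working it through.** **1. The plan's own figure.** Section 4.2 gives a follow-up period of 1 week to 10 days. From the end of the treatment week (Day 7) to the last visit (Day 14 to 17): 14 − 7 = 7 and 17 − 7 = 10 days. It reproduces.

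**2. Completers, from the last dose (Day 5).** 14 − 5 = 9 and 17 − 5 = 12 days nominal. Dialysis falls on Days 1, 3, 5, 8, 10 and 12; the same weekly pattern continues to Days 15 and 17. Day 14 is a Sunday on the Monday schedule and a Monday on the Tuesday schedule, so it is a dialysis day on neither. A visit on a dialysis day gives 15 − 5 = 10 or 17 − 5 = 12 days.

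**3. Early leavers.** Days observed = day of last visit − day of last dose, with visits on dialysis days up to Day 12.

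| Last dose | Last visit at next dialysis | Days observed | If the last visit is later |
|---|---|---|---|
| Day 1 | Day 3 | 3 − 1 = 2 | 4, 7, 9 or 11 |
| Day 3 | Day 5 | 5 − 3 = 2 | 5, 7 or 9 |
| Day 5 | Day 8 | 8 − 5 = 3 | 5 or 7 |

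The permitted range is 2–11 days, with a floor of 2–3.

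**4. From the first dose, which is how Section 12.10.1 counts AEs.** A subject closed out on Day 3 has 3 − 1 = 2 days. A completer has 14 − 1 = 13 to 17 − 1 = 16 days.

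**5. The same event in two subjects.** Take an SAE with onset on Day 6. In a subject still in the study it is entered in the eCRF and tabulated. In a subject closed out on Day 3 it is reportable but kept out of the eCRF. Section 15 has all required study data entered in the eCRF, so the inference is that this SAE misses the Section 12.10.1 tables. A new non-serious AE on Day 6 in the second subject is not collected at all.

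**6. SAE reporting, from the last dose.** Earliest leavers: 3 + 30 − 1 = 32, 5 + 30 − 3 = 32 and 8 + 30 − 5 = 33 days. Completers: 14 + 30 − 5 = 39 to 17 + 30 − 5 = 42 days.

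**7. Scale.** The documents give no withdrawal rate, so the number leaving at the 2-day floor, k of 30, is an assumption. The share of post-last-dose follow-up lost is k(10 − 2)/(30 × 10) if completers have 10 days, or k(12 − 2)/(30 × 12) if they have 12.

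| k (assumed) | Completers at 10 days | Completers at 12 days |
|---|---|---|
| 1 | 8/300 = 2.7% | 10/360 = 2.8% |
| 3 | 24/300 = 8.0% | 30/360 = 8.3% |
| 5 | 40/300 = 13.3% | 50/360 = 13.9% |

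These are shares of observation time, not of events.

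**The case against.** The strongest reply is that little is lost.

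- **The AE that causes withdrawal precedes close-out and is already counted.** This stands. Since a subject counts once per system organ class or preferred term, only a new and different event after close-out is lost.
- **Safety oversight continues.** This also stands. SAEs remain reportable for 30 days, related SAEs at any later time, and known AEs are followed. The gap concerns new non-serious AEs and the eCRF-based tables.
- **The eCRF rule applies to everyone.** True, but it takes effect earlier for an early leaver.
- **Stopping the drug need not mean leaving the study.** Section 5.4.1 says subjects may be withdrawn, and Section 12.6 tabulates those given 1, 2 or 3 doses. No text says whether a subject who stops dosing can stay to Day 14, so the point is confined to subjects who leave.
- **Section 10.3 mentions telephone contacts and extra tests.** It does so for assessing an AE the subject has reported. It sets no period for finding new ones.
- **Collecting to Day 14–17 would over-observe early stoppers, at 13–16 days after a last dose on Day 1.** Measured from the last dose, yes. Because the tables count from the first dose, a common end date gives all dosed subjects the same 13–16 day window.

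A reader might also infer that much of the drug is still present when collection closes, taking the whole half-life range of "34.1 to 39.0 hours after the first dose and 40.0 to 49.3 hours after the third dose". The upper values belong to the third dose. At 48 hours after a first dose, 2^(−48/34.1) = 0.38 and 2^(−48/39.0) = 0.43. With the half-life of about 24 hours in Section 1.1 it is 2^(−48/24) = 0.25. These figures ignore dialysis and the rapid initial phase, and the point does not rest on them.

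**Conclusion.** The point holds as a gap in the AE collection rule. Following the text, dosed subjects share one denominator but may be observed for 2–11 days after the last dose if they leave early, against a nominal 9–12 if they complete. No other section provides for collecting new AEs after an early close-out. The likely effect is a modest understatement of AE incidence, and of SAE incidence in eCRF-based tables.

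This rests on three assumptions: that the early visit takes place at a dialysis session, that the tables are built from the eCRF, and that some dosed subjects leave early. The separate SAP announced in Section 12.1 could bring in SAEs from the safety database, but no analysis rule can recover AEs that were never collected.

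Two stronger readings are not supported. A reader might infer that early leavers typically get 2 days; that is the floor, since the documents give no timing for the early visit. A reader might also take one subject in 30, or 3.3 percentage points, as the bias; that is only the weight of one subject, and the documents give neither a withdrawal rate nor an event rate after close-out. In a small descriptive study with three doses, this is a cheap improvement rather than a threat to the primary objective.

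**What to change.** - **Section 10.2:** for every subject who received at least one dose, collect new AEs and SAEs and enter them in the eCRF until the subject's scheduled Day 14 (+3 days) date or the early-termination visit, whichever is later. Collect by telephone if no visit takes place, unless the subject refuses further contact.
- **Section 10.7.2:** let the rule confining SAEs to the safety database apply only after that date.
- **Section 5.4.1:** replace the pointer to Section 10.3 with one to this follow-up.

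The cost is protocol wording, about one telephone contact per early leaver, and an eCRF open up to about two weeks longer for that subject (Day 3 to Day 17 is 14 days). Telephone AE reporting appears in Section 8.1 only for extraordinary events, so its use here must be written in. Nothing changes for completers.
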